5.2.1. Validated Investigator Global Assessment Scale for Atopic Dermatitis

Validated Investigator Global Assessment scale for Atopic Dermatitis (vIGA-AD) assessments should be completed prior to other physician assessments.

vIGA-AD assessment will be performed according to the Schedule of Visits and Assessments (Section 1.3). The vIGA-AD is a static evaluation of qualitative overall AD severity. This global assessment scale is an ordinal scale with five severity grades (reported only in integers of 0 to 4). Each grade is defined by a distinct and clinically relevant morphologic description that minimizes inter-observer variability (see Error! Reference source not found.). vIGA-AD is evaluated for the entire body except the scalp, palms, and soles.

Note: All atopic dermatitis lesions on a subject will be treated including the face, trunk, genitals/skin folds, or limbs (excluding the scalp). The palms and soles will be treated but will not be counted towards any measurements of efficacy (EASI, vIGA-AD, BSA).

Every effort must be made for the same Evaluator to complete the IGA for the subject at every study visit.

IGA will be assessed at clinic visits prior to the subject applying Investigational Product at the site.

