5.5 Derived Variables

All questionnaire scores will be derived by Biostatistics in the ADaM datasets using the formulas defined below, even if calculated scores are present in the EDC database. All pre-calculated scores will be ignored for analysis.

	STATISTICAL ANALYSIS PLAN, Version 3.0
Protocol Number: ARQ-151-311	Sponsor: Arcutis Biotherapeutics, Inc.

- With the following exception, vIGA-AD Success = vIGA-AD of ‘Clear’ (0) or ‘Almost Clear’ (1) plus at least a 2-grade improvement from Baseline. The exception is that for subjects who discontinued early from study due to an AE or lack of efficacy, the subject will be considered as not having a vIGA-AD success (for MI and non-responder imputation analyses) or missing (for observed case analyses) for all pre-specified analysis visits (refer to Section 5.4) for which the subject’s last dose day falls within analysis visit window or is prior to the start of the analysis visit window.
- Average weekly WI-NRS = Average weekly WI-NRS pruritus score will be calculated as the sum of the daily WI-NRS scores reported during a specific week (in a 7-day period; refer to Section 5.4) of the study divided by the number of days with non-missing scores for that week. A minimum of 4 days of observations are needed to calculate an average weekly WI-NRS pruritus score. Otherwise, the corresponding average weekly WI-NRS pruritus score will be considered missing.
- With the following exception, a WI-NRS 4-point reduction = achievement of a 4- point reduction in average weekly WI-NRS pruritus score compared to average weekly WI-NRS baseline, calculated only for the subjects ≥ 12 years old with average weekly WI-NRS score of ≥ 4 at baseline. The exception is that for subjects who discontinued early from study due to an AE or lack of efficacy, the subject will be considered as not having a WI-NRS 4- point reduction (for MI and non-responder imputation analyses) or missing (for observed case analyses) for all pre-specified analysis visits (refer to Section 5.4) for which the subject’s last dose day falls within the analysis visit window or is prior to the start of the analysis visit window.
- EASI total score = $0.1 (E_h + I_h + E_{Xh} + L_h) A_h + 0.2 (E_u + I_u + E_{Xu} + L_u) A_u + 0.3 (E_t + I_t + E_{Xt} + L_t) A_t + 0.4 (E_l + I_l + E_{Xl} + L_l) A_l$
for subjects ‘ ≥ 8 years old’
and

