6.2.1 Multiple Imputation

All subjects, regardless of completion status, will have available data assigned to the pre-specified analysis visit using the analysis windows defined in Section [5.4](#), including the last available data

	STATISTICAL ANALYSIS PLAN, Version 3.0
Protocol Number: ARQ-151-311	Sponsor: Arcutis Biotherapeutics, Inc.

of subjects who prematurely withdraws from the study. To comply with the definition of the primary estimand (Section 12.1.1), for subjects who discontinue due to lack of efficacy or adverse event, efficacy data assigned to a pre-specified analysis visit will be removed from the source data used for the multiple imputation process if subject's last dose day falls within the analysis visit window or is prior to the start of the analysis visit window used to assign data to a pre-specified analysis visit. Similarly, WI-NRS weekly averages will be removed from the source data used for multiple imputation if subject's last dose day falls within the analysis visit window or is prior to the start of the interval used to compute the weekly average as defined in Section 5.4. This procedure will ensure that the data collected on or after intercurrent events are not used in the imputation process.

For the primary efficacy endpoint of vIGA-AD success at Week 4 and the secondary endpoint of vIGA-AD success at Week 4 among subjects with a 'Moderate' randomized vIGA-AD score, the primary analysis will impute missing values using a Predictive Mean Matching (PMM) sequential-regression multiple imputation model for the ITT population. This is a three-step process.

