6.2.3 Tipping Point Analysis

As a sensitivity analysis to the multiple imputation analysis as described in Section 6.2.1 for the vIGA-AD success primary endpoint and secondary endpoint of vIGA-AD success among subjects with Moderate disease at baseline, a tipping point analysis will be performed in order to determine the inflection point at which the inference under the missing not at random (MNAR) assumption changes substantially.

The sensitivity analysis for the primary endpoint will be performed by using a specified sequence of shift parameters. The range of shift parameters to be included in this analysis are 0 to 2 by 0.2 for active and -2 to 0 by 0.2 for Vehicle. The values at which the results of the primary analysis are shifted from significant (i.e., $\alpha \leq 0.05$) to non-significant (i.e., $\alpha > 0.05$) will be determined. Steps 1 and 3 of the analysis will be the same as for the multiple imputation analysis as described in Section 6.2.1. However, Step 2 of the analysis is where the shift parameters will be applied.

Imputed values for subjects who discontinue due to lack of efficacy or adverse event will be handled as described in Step 2 of Section 6.2.1 to ensure that these subjects are analyzed as non-responders at all visits on or after discontinuation of treatment.

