12 EFFICACY ANALYSIS

12.1 Primary Efficacy Endpoint Analysis

12.1.1 Primary Efficacy Endpoint and Estimand

The vIGA-AD is a static evaluation of qualitative overall AD severity. This global assessment scale is an ordinal scale with five severity grades (reported only in integers of 0 to 4). Each grade is defined by a distinct and clinically relevant morphologic description that minimizes inter-observer variability. vIGA-AD is evaluated for the entire body except the scalp, palms, and soles.

The primary efficacy endpoint is vIGA-AD success, defined as an vIGA-AD score of ‘clear’ (0) or ‘almost clear’ (1) plus at least a 2-grade improvement from Baseline at Week 4.

The primary estimand is described by the following attributes:

Population: Patients with Atopic Dermatitis

Endpoint: vIGA-AD success at Week 4

Intercurrent events: In the course of the 4-week randomized treatment period, subjects may be exposed to possible known or unknown intercurrent events that could possibly impact the estimates of the estimand, such as treatment discontinuation due to a specific adverse effect or perhaps a lack of effect. A composite strategy will be implemented that handles subjects who discontinue due to lack of efficacy or adverse event as missing not at random differently than all other subjects. That is, subjects who discontinue due to lack of efficacy or adverse event will be treated as non-responders for all pre-specified analysis visits (refer to Section 5.4) for which the subject’s last dose day falls within the analysis window or is prior to the start of the analysis window (refer to

	STATISTICAL ANALYSIS PLAN, Version 3.0
Protocol Number: ARQ-151-311	Sponsor: Arcutis Biotherapeutics, Inc.

Section 5.5) while the “Treatment Policy Strategy” will be adopted for handling intercurrent events in this study other than discontinuation due to lack of efficacy or adverse event.

Population-level summary: ratio of the odds of achieving vIGA-AD success after 4 weeks of using roflumilast cream 0.15%, relative to the odds of success after 4 weeks using a matching vehicle cream in the ITT population.

The supportive population-level summary: the proportion difference between Roflumilast cream 0.15% and vehicle groups will be provided for the patients who achieve vIGA-AD success at week 4 in the ITT population.

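### The AE/lack-of-efficacy rule tests last dose against the visit window, not the assessment date, so some on-treatment Week 1 and Week 2 vIGA-AD successes are scored as failures

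*SAP*

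**What the plan says.** SAP 12.1.1 adopts a composite strategy: "subjects who discontinue due to lack of efficacy or adverse event will be treated as non-responders for all pre-specified analysis visits" that meet a last-dose condition. SAP 5.5 states that condition for vIGA-AD success. The visit fails if the subject's "last dose day falls within analysis visit window or is prior to the start of the analysis visit window". The consequence is non-response in the multiple-imputation (MI) and non-responder analyses, and a missing value in observed-case analyses. SAP 5.5 repeats the rule for the 4-point WI-NRS reduction and the EASI thresholds. It has no such exception for vIGA-AD clear or almost clear.

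SAP 6.2.1 applies the same test to the imputation inputs: "efficacy data assigned to a pre-specified analysis visit will be removed from the source data used for the multiple imputation process". It gives the purpose as "This procedure will ensure that the data collected on or after intercurrent events are not used in the imputation process". SAP 6.2.3 describes the aim as "to ensure that these subjects are analyzed as non-responders at all visits on or after discontinuation of treatment".

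For weekly WI-NRS, the second limb of the test in SAP 6.2.1 is different. It asks whether the last dose is "prior to the start of the interval used to compute the weekly average", where SAP 5.5 refers to the start of the analysis visit window.

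**The concern.** The visit windows in SAP 5.4, Table 2 extend beyond the target days: Week 1 to Day 11 and Week 2 to Day 22. A subject can be assessed, continue dosing for several days, stop for an AE, and still have a last dose inside the window of the visit already completed. That earlier result is then discarded and counted as a failure, although it was seen before the event.

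The Week 1 and Week 2 responder endpoints are alpha-controlled (SAP 6.5 and 12.2). WI-NRS at Weeks 2 and 1 is in Family 1, and vIGA-AD success at Weeks 2 and 1 is in Family 2. All three Family 1 tests must succeed before their 0.03 passes to Family 2. An early itch result can therefore decide whether EASI-75 at Week 4 is tested at 0.02 or 0.05.

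**Working it through.** The plan states no figure for this point, so there is nothing to reproduce. The check applies the rule to each possible last-dose day.

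**Inputs**
- SAP Table 2: Week 1 is Days 2-11 (target 8), Week 2 is Days 12-22 (target 15), Week 4 is Days 23-43 (target 29).
- SAP Table 4 (weekly WI-NRS): Week 1 is Days 1-7, Week 2 is Days 8-14.
- Visit tolerance of 3 days either way (schedule of visits).
- Order on a visit day (Protocol 5.2.1): "IGA will be assessed at clinic visits prior to the subject applying Investigational Product at the site". No application takes place in clinic at Day 29/ET (SAP 3.2).

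**vIGA-AD success.** Let L be the last-dose day, v the assessment day and U the upper limit of the window. Within the window, or before it starts, reduces to L ≤ U. The assessment is on treatment if v ≤ L, because it precedes that day's application. An on-treatment result is therefore failed when v ≤ L ≤ U, which covers U − v + 1 days.

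| Visit | Seen on day | Last-dose days affected | Count |
|---|---|---|---|
| Week 1 | 5 | 5-11 | 7 |
| Week 1 | 8 | 8-11 | 4 |
| Week 1 | 11 | 11 | 1 |
| Week 2 | 12 | 12-22 | 11 |
| Week 2 | 15 | 15-22 | 8 |
| Week 2 | 18 | 18-22 | 5 |

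Leaving out same-day dosing, the on-target counts are 3 and 7. Example: success on Day 15, dosing to Day 20, then a stop for an AE. Since 20 ≤ 22, the Day 15 success becomes a Week 2 failure.

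**Week 4.** Every last-dose day in the table is before Day 23, so these subjects are Week 4 failures whether the rule uses windows or dates.

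**Size.** The documents give no rate of AE/lack-of-efficacy stops. Assume 1-5%, spread evenly over Days 1-28, visits on target, and every deleted result a success:
- Week 1: 4/28 = 14% of such stops. 1% × 4/28 = 0.14 points; 5% × 4/28 = 0.71 points.
- Week 2: 8/28 = 29% of such stops. 1% × 8/28 = 0.29 points; 5% × 8/28 = 1.43 points.
- At 2%, with 650 × 2/3 = 433 active subjects, there are 8.7 stops, of which about 1.2 affect Week 1 and 2.5 affect Week 2.

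**Clear or almost clear at Weeks 1 and 2.** SAP 6.2.1 deletes the observed score, but SAP 5.5 has no rule that fails the visit. The main analysis would therefore impute a value in place of an observed on-treatment score. The non-responder analysis (SAP 6.2.2) uses the score at that visit.

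**Weekly WI-NRS.** The result depends on which table defines the analysis visit window.
- Table 2: the Week 1 average fails if L ≤ 11, so a fully treated week (L ≥ 7) is failed for Days 7-11. The Week 2 average fails if L ≤ 22, so a fully treated week (L ≥ 14) is failed for Days 14-22. For L on Days 8-11, SAP 5.5 fails Week 2 because L is before Day 12. SAP 6.2.1 keeps the Week 2 average as imputation input, because L is neither in Days 12-22 nor before Day 8.
- Table 4: a fully treated week is failed only for a last dose on Day 7 (Week 1) or Day 14 (Week 2), and the Days 8-11 disagreement disappears.

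**The case against.** The strongest reply is that the rule is deliberate. It appears in matching form in SAP 5.5, 6.2.1 and 12.1.1. The purpose in SAP 6.2.1 is met, since nothing collected after the event is used, and the text does not promise to spare everything earlier. If the unit is the analysis visit, the visit whose window contains the last dose is arguably the visit at which discontinuation occurs. This stands to the extent that the SAP breaks no explicit promise. It does not explain why a Day 15 score should be failed for an event on Day 20. The regulatory advice quoted in SAP 1 concerns the primary estimand and does not ask for earlier visits to be failed.

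On itch, Table 4 is titled for weekly WI-NRS, and SAP 5.5 defines the average over a 7-day period with a reference to SAP 5.4. Against that, Table 2 is titled for efficacy endpoints in general. A reader might infer that SAP 5.5 and 6.2.1 flatly contradict each other on itch. The documents support that only under Table 2, and they do not settle which table applies.

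It is also fair to object that a rule based on dates alone would weaken the composite strategy. A subject who stops on Day 16 with no Week 4 assessment has no date to compare, and would pass to imputation. That stands, and the fix provides for it.

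Finally, the effect is small. Lack-of-efficacy stops will seldom follow a recorded success, and in Family 2 the early vIGA-AD endpoints are tested only after EASI-75 and clear or almost clear at Week 4.

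**Conclusion.** The concern holds in a limited form and is worth correcting. For subjects who stop for an AE or lack of efficacy, the window test discards some vIGA-AD successes observed on treatment at Weeks 1 and 2. It scores them as failures in the MI and non-responder analyses and as missing in observed-case analyses. The treatment of clear or almost clear is incomplete, and the itch window is not defined.

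The loss is at most 0.14-0.71 points per arm at Week 1 and 0.29-1.43 points at Week 2. This rests on the assumed 1-5% rate, even spacing and on-target visits. Earlier visits or clustered stops would raise it, up to the discontinuation rate itself. It lowers the rate more in the arm with more such stops, so its direction cannot be known in advance.

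Three stronger readings are tempting but unsupported:
- **That the primary analysis is compromised.** These subjects are Week 4 non-responders under either rule.
- **That more than half of such stops are affected.** Pooling both visits over Days 8-28 gives 12/21 = 57%, but each endpoint is exposed through one window only: 14% or 29% of stops over Days 1-28.
- **That every early endpoint is scored as a failure.** Clear or almost clear is imputed in the main analysis.

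**What to change.** In SAP 5.5, 6.2.1 and 12.1.1, for subjects who discontinue due to an AE or lack of efficacy:
- Score a visit as non-response, and remove its data from the imputation source, if the assessment used for that visit was made after the last dose, or if no assessment exists for that visit and the last dose is within or before its window.
- Keep assessments made on or before the last-dose day.
- For weekly WI-NRS, name the Table 4 interval in both 5.5 and 6.2.1, and apply the rule when the last dose is before the interval's final day.
- Apply the same rule to vIGA-AD clear or almost clear.

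Visits after the last dose remain failures, so the composite strategy is preserved. The cost is wording in three sections and one derivation. SAP 1 places this version before database lock and unblinding, and the change should be made on that side of unblinding. If the sponsor intends the broader window rule, the aims in SAP 6.2.1 and 6.2.3 should be reworded to say so, and the WI-NRS window still has to be named.

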5.6 Descriptive Statistics

All continuous variables will be summarized by presenting the number of subjects, mean, standard deviation (SD), median, Q1, Q3, minimum, and maximum. For PK endpoints, geometric statistics including geometric mean and coefficient of variation (CV) will also be provided.

Categorical variables will be presented as frequencies and percentages.

Summary tables will be presented by visit, when applicable.

Change from baseline will be calculated as:

	STATISTICAL ANALYSIS PLAN, Version 3.0
Protocol Number: ARQ-151-311	Sponsor: Arcutis Biotherapeutics, Inc.

Assessment value at postbaseline visit X – baseline value.

Percent change from baseline will be calculated as:

$$(\text{Assessment value at postbaseline visit X} - \text{baseline value}) \times 100\% / (\text{baseline value})$$

Percent change from baseline will be missing in situation where baseline value equals to 0.

5.7 Statistical Tests

Unless otherwise specified, all statistical tests will be two-sided and will be performed with a significant level of 0.05. Confidence intervals (CIs) will be two-sided with 95% coverage.

5.8 Handling of Retests, Unscheduled Visits, and Early Termination Data

Retests measurements, Unscheduled measurements, and ET visit assessments will be included in analysis and be summarized via analysis visit windowing according to the windowing conventions in section 5.4.

All data from retest, unscheduled measurements and ET visit assessments will be listed.

5.9 Software Version

All analyses will be performed using SAS® software Version 9.4 or higher.

6 STATISTICAL CONSIDERATIONS

6.1 Adjustments for Covariates

Covariates for this study include pooled study site and baseline vIGA-AD (vIGA-AD=2 - Mild vs. vIGA-AD=3 - Moderate at randomization). Subgroup analyses will be generated for the baseline covariates.

